### **2.5.2. Peak Nasal Inspiratory Flow**

Peak nasal inspiratory flow is collected in both Part 1 and Part 2, but the timing of the collection is different between the parts. For Part 1, the data is collected for observation only. For Part 2, the data is collected as an exploratory efficacy endpoint.

Pre-NAC adjusted value is defined as the observed value minus 0 minutes prior NAC value.

The peak nasal inspiratory flow will be summarized using summary statistics for:

- The observed value at each time point,
- The Pre-NAC adjusted value at each time point,
- the Observed Area Under the Curve from 0 to 120 minutes Post NAC, and
- the Pre-NAC adjusted Area Under the Curve from 0 to 120 minutes Post NAC.

For Part 2, observed values and change between Visits 3 and 4 will be summarized for the indicated items.

The collected data will be summarized using descriptive statistics at each time point in which the assessment was collected. Observed and change from baseline values will be summarized. Post-baseline values will be analyzed using an Analysis of Covariance to test for treatment effect where treatment is the main factor and Visit 3 value as the covariate.

### **2.5.3. Nasal Inflammation Score**

The nasal inflammation score is collected in both Part 1 and Part 2, but the timing of the collection is different between the parts. For Part 1, the data is collected for observation only. For Part 2, the data is collected as an exploratory efficacy endpoint.

Pre-NAC adjusted value is defined as the observed value minus 0 minutes prior NAC value.

The nasal inflammation score will be summarized using summary statistics for:

- The observed value at Pre-NAC and 120 minutes Post-NAC, and
- The Pre-NAC adjusted value at 120 minutes Post-NAC,

For Part 2, observed values and change between Visits 3 and 4 will be summarized for the indicated items.

The collected data will be summarized using frequency counts at each time point in which the assessment was collected. Observed values will be summarized. A Cochran-Mantel-Haenszel test will be conducted at each post-baseline visit to test for treatment effect.

#### **2.5.4. Intranasal Nitric Oxide**

Intranasal nitric oxide is collected in both Part 1 and Part 2, but the timing of the collection is different between the parts. For Part 1, the data is collected for observation only. For Part 2, the data is collected as an exploratory efficacy endpoint.

Pre-NAC adjusted value is defined as the observed value minus 0 minutes prior NAC value.

Intranasal Nitric Oxide will be summarized using summary statistics for:

- The observed value at Pre-NAC and 120 minutes Post-NAC, and
- The Pre-NAC adjusted value at 120 minutes Post-NAC,

For Part 2, observed values and change between Visits 3 and 4 will be summarized for the indicated items.

The collected data will be summarized using descriptive statistics at each time point in which the assessment was collected. Observed and change from baseline values will be summarized. Post-baseline values will be analyzed using an Analysis of Covariance to test for treatment effect where treatment is the main factor and Visit 3 value as the covariate.

#### **2.6. Interim Analyses and Database Lock**

There are no interim analyses planned for this study. There will be a database lock after each of the parts are completed. The unblinding and analysis of the data will be performed for each part after their respective database lock.

##### **2.6.1. Part 1 Database Lock**

The Part 1 database lock will take place after all part 1 subjects have completed the study.

##### **2.6.2. Part 2 Database Lock**

The Part 2 database lock will take place after all part 2 subjects have completed the study.

#### **2.7. Sample Size and Power Considerations**

Part 1 (safety and tolerability evaluation in healthy volunteers) will enroll 24 subjects. Up to 12 subjects per dose cohort (n=8 active, n=4 vehicle) will be enrolled, with a target of 20 subjects completed (10 subjects per dose cohort; n=7 active, n=3 vehicle) assuming a 16.7% drop out rate. The two dose cohorts are  $1 \times 10^9$  cells/ml and  $4 \times 10^9$  cells/ml.

Part 2 (preliminary efficacy evaluation in subjects with a history of SAR to ragweed pollen) will enroll 42 subjects. Up to 14 subjects per arm ( $1 \times 10^9$  cells/ml;  $4 \times 10^9$  cells/ml or vehicle) will be enrolled, with a target of 12 subjects per arm for a total of 36 subjects completed, assuming a 10-15% drop-out rate.

The sample size for this study is not based on statistical considerations.

## 2.8. Handling Missing Data

Listings will be provided for all data. Descriptive statistics will be provided for all planned visits as provided on the eCRFs. No imputations for missing data will be used in the data displayed in the listings such that the listing will only show “observed data”.

### Safety and Other Rules

Per the protocol, visits are expected to occur within a given number days of the expected day of the visit. The visits will be analyzed as recorded. Likewise, unscheduled visits will not be reassigned a visit number based on the visit date.

Dates related to the adverse events and medications will be imputed using the rules below in an effort to categorize them properly into the summary tables.

Imputing partial or missing start dates:

- If the year is unknown, then the start date will not be imputed. The date will remain missing.
- If the month is unknown and the year is the same as the first injection date of the study, then impute the month and day of the date to be equal to the first injection month and day. Otherwise, impute the month as January.
- If the day is unknown and the month and year are the same as the first injection date of the study, then impute the day to be equal to the day of the first injection. Otherwise, impute the day as ‘01’.

Impute partial or missing stop dates:

- If the year is unknown, then the stop date will not be imputed. The date will remain missing.
- If the month is unknown, impute the month as December.
- If the day is unknown, impute the day to be the last day of the month.

If an imputed stop date is greater than the date of study completion/discontinuation date of the study, then the imputed stop date will be set equal to the date of completion/discontinuation date.

The imputed dates will be stored in the analysis datasets along with the original dates as recorded by the sites.

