7.3 Study Withdrawal and Withdrawal from Investigational Product and Stopping Criteria

A participant may withdraw from the study at any time at his/her own request, or may be withdrawn at any time at the discretion of the Investigator.

Reasons for withdrawal (participants who refuse to complete any remaining study visits) or discontinuation (participants who prematurely stop the application) at any time during the study may include, but are not limited, to the following:

- For safety reasons, either at the discretion of the Investigator or at the participant's request
- For protocol violations at the discretion of AOBiome
- Due to concomitant therapy that could interfere with the results of the study (the Investigator will report all such information on the CRFs and decide, in accordance with AOBiome, whether the participant is to be withdrawn).

The reason for participant study withdrawal will be recorded in the electronic Case Report Form (eCRF). Data from participants withdrawing from the study will be considered evaluable up to the point at which they are withdrawn using the same criteria for evaluability as for participants who complete the study.

For Part 1 safety evaluation and Part 2 preliminary efficacy , AOBiome will include study stopping rules to pause study for safety review in the event that ~~t1~~ subject reports a SAE, ~~t2~~ grade 3 (severe) AEs, or ~~t3~~ grade 2 (moderate) AEs considered possibly, probably, or definitely related to the investigational product.

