7.5 Early Termination

Participants who have discontinued the study early will be evaluated by the Investigator at the Unanticipated Visit. See the list of assessments to be performed at the Unanticipated Visit in the Schedule of Events Table (Appendix A). Participants with ongoing AEs or SAEs believed to be possibly related to investigational product (IP) will continue to be followed until resolution or for 30 days as warranted by the nature of the AE.

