10.6.5 Unscheduled/Unanticipated Study Visit

If an event arises that requires patient to come in to the research center, subjects should be scheduled for the Unscheduled visit.

During the visit, the following will be obtained:

- medical/surgical history
- record concomitant medications
- obtain in clinic blood pressure, heart rate, respiratory rate
- physical exam
- body weight
- nasal inspection
- obtain study medication weight for Investigational Product compliance
- study counseling
- laboratory testing (blood for metabolic panel, hematology, clinical chemistry, liver function test, urinalysis)
- study AEs
- nasal fluid collection for biomarkers
- blood collection for biomarkers
- peak nasal inspiratory flow (PNIF)
- intranasal nitric oxide
- nasal inflammation score
- study diary

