14.4 Safety Analyses

14.4.1 Definitions

All adverse events recorded during the study will be coded according to Medical Dictionary for Regulatory Activities.

The primary analysis of safety will be based on the safety population, which is defined as all subjects receiving at least 1 dose of B244 or placebo. Adverse events (AEs) will be coded using the Medical Dictionary for Regulatory Activities (MedDRA®) for purposes of summarization. All AEs occurring during the study will be included in by-subject data listings and tabulated. Events leading to death, SAEs, and events resulting in study discontinuation will be summarized using standard descriptive statistics, and presented by treatment arm. Exposure to study drug and reasons for discontinuation of study treatment will be tabulated. Shift tables relative to the normal range will be provided for laboratory parameters. Additional analyses will be performed, if warranted, upon review of the data.

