#### **2.4.3. Vital Signs**

Blood pressure, heart rate, and respiration rate will be measured at each visit. Observed and change from baseline values will be summarized using descriptive statistics. All vital signs will be shown in data listings.

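### Vital signs and laboratory values that early terminators give at the Unanticipated Visit are listed, but no specified SAP summary table includes them

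*SAP*

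**What the plan says.** **Where early terminators are seen.** Protocol 7.5: "Participants who have discontinued the study early will be evaluated by the Investigator at the Unanticipated Visit". Protocol 12.6 sends subjects who withdraw to the same set of assessments. No separate early-termination visit is described.

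**What is measured there.** The list in Protocol 10.6.5 includes "obtain in clinic blood pressure, heart rate, respiratory rate" as well as haematology, chemistry, liver function and urinalysis. Protocol 11.9 confirms that laboratory assessments are made at an Unanticipated Visit.

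**What the SAP summarises.** SAP 2.8: "Descriptive statistics will be provided for all planned visits as provided on the eCRFs". Under its Safety and Other Rules: "Likewise, unscheduled visits will not be reassigned a visit number based on the visit date". For vital signs, SAP 2.4.3 says: "Observed and change from baseline values will be summarized using descriptive statistics". SAP 2.4.2 treats haematology and chemistry in the same way, gives frequency counts for urinalysis, and lists out-of-range results separately. SAP 3.2 puts all data in listings.

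**What the protocol promises.** Protocol 14.4.1: "Shift tables relative to the normal range will be provided for laboratory parameters". Protocol 14.3 calls for actual values and changes from baseline for laboratory tests and vital signs at every evaluation made on study. Neither promise is limited to planned visits.

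**The concern.** Read together, these rules collect a safety measurement at the moment a subject leaves and then give it no place in the tables that compare B244 with vehicle. Vital signs are a named component of the Part 1 primary endpoint and of the Part 2 secondary safety endpoint. Laboratory values are not named in those endpoints, but SAP 2.4 lists them as a safety parameter.

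Subjects may leave for safety reasons (Protocol 7.3), and those who need rescue medication must be terminated (Protocol 8.14), so leaving need not be unrelated to these measurements. If it is related, the change-from-baseline tables describe mainly the subjects who stayed, and the values closest to the reason for stopping have to be found in a listing.

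**Working it through.** **1. The plan's own drop-out figures** (Protocol 14.1, SAP 2.7).

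- Part 1: 24 enrolled, 20 completing. 4/24 = 16.7%, as stated; equivalently 20/(1 − 1/6) = 24.
- Part 2: 42 enrolled, 36 completing. 6/42 = 14.3%, inside the stated 10-15%; 36/0.90 = 40 and 36/0.85 = 42.4.
- Both parts: (4 + 6)/(24 + 42) = 10/66 = 15.2%.

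**2. Planned visits that could carry a post-dose value** (Protocol 10.5, 10.6, 11.9).

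| | Laboratory tests | Vital signs |
|---|---|---|
| Part 1 | Screening, Day 14, Day 42 | Screening, Visit 2 before and after the first dose, Days 14, 21 and 42 |
| Part 2 | Screening, Visit 4 | Screening, Visit 3 (the dosing visit, no post-dose reading specified), Visit 4 |

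**3. What remains in the tables for an early leaver.**

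- Part 2: a randomised subject who misses Visit 4 has no planned laboratory or vital-sign record after the dosing visit. The Unanticipated Visit is the only one.
- Part 1, stopping before Day 14: no planned post-dose laboratory result. The vital signs taken after the first dose at Visit 2 stay in.
- Part 1, leaving after Day 14: the Day 14 results stay in, and so do the Day 21 vital signs if that visit was attended.

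**4. Size.** If all planned non-completers leave before the end-of-treatment visit, the post-dose laboratory summaries rest on at most 24 − 4 = 20 of 24 subjects and 42 − 6 = 36 of 42. Including the Unanticipated Visit could raise these to 24 of 24 and 42 of 42, if every early terminator attends it. The Part 1 count is an upper bound, because completion there runs to Day 42 (Protocol 12.4) and some of the 4 may leave during follow-up.

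**5. Effect on an arm mean.** Let f be the share of an arm whose only post-dose value is unplanned, m_E their mean change and m_C the mean change of the others. The mean over everyone is (1 − f)·m_C + f·m_E, and the table shows m_C, so the table is off by f·(m_E − m_C). With the pooled planned shares, f is at most 4/24 = 0.167 in Part 1 and is 6/42 = 0.143 in Part 2. The documents give no value for m_E − m_C. The comparison between arms depends on the difference of two such terms, so its sign is not determined.

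**6. Search for another table.** The SAP 4.1 titles for laboratory tests (14.3.2.1 to 14.3.2.4) and vital signs (14.3.3) are general summaries. No title mentions shifts, last values, worst values or early termination. SAP 2.9 covers withdrawals through disposition and adverse event outputs only.

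**The case against.** **The loss is narrower than it first looks.** A reader might infer that early terminators vanish from every safety summary. The documents do not support that. The adverse event, SAE and discontinuation tables (SAP 2.4.1, tables 14.3.1.1 to 14.3.1.8) do not depend on visit number. A blood pressure or laboratory change serious enough to cause stopping would ordinarily be recorded as an adverse event and tabulated by arm. Values from planned visits already attended also stay. All of this stands.

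**The SAP does not say that only planned visits are summarised.** It says visits are analysed as recorded, and declining to renumber a visit does not forbid a separate row for it. The table-shell section available here gives only rules on decimal places, so row-level content cannot be checked. This stands as a caution, which is why the point concerns *specified* tables. But no such row is specified, and a visit triggered by an event, with no study day, does not fit naturally among planned visits.

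**Not renumbering is defensible.** It keeps, say, a Day 3 value out of the Day 14 row. Agreed, and the fix leaves that rule alone.

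**Protocol 7.3.** A reader might also see a contradiction with its statement that withdrawn subjects' data "will be considered evaluable up to the point at which they are withdrawn using the same criteria for evaluability". That is arguable at best: the sentence runs only up to withdrawal, the Unanticipated Visit follows discontinuation, and the SAP's rule applies equally to completers.

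**The shift tables are a separate mismatch.** True: they concern all subjects. They belong here because they are the promised laboratory table that could include unscheduled records.

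**Conclusion.** The concern holds in a limited form. Vital signs and laboratory values from the Unanticipated Visit are collected and listed but have no specified place in the SAP's summary tables. The SAP also omits the shift tables of Protocol 14.4.1 and does not deliver the scope of Protocol 14.3.

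On the planned drop-out this touches at most 4 of 24 and 6 of 42 subjects. It is sharpest in Part 2, where the omitted record is an early leaver's only one after the dosing visit, and for Part 1 laboratory values before Day 14. These counts assume that drop-out runs as planned and that leavers attend the Unanticipated Visit; a leaver who does not attend has no value to omit.

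It would be tempting to conclude that the safety comparison is biased toward no difference. The documents do not show that. Understatement follows only if stopping is related to a treatment effect on these measures, and losses on vehicle could shift the comparison too. This is a worthwhile, inexpensive correction rather than a flaw that undermines the primary safety assessment.

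**What to change.** Before the database lock and unblinding of each part, amend SAP 2.4.2 and 2.4.3 and the table list as follows.

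- Keep the by-visit rows and the rule against renumbering unscheduled visits.
- Add, by arm, a separate row for the last post-baseline value of each vital sign and laboratory parameter, counting the Unanticipated or early-termination visit.
- Add, by arm, the worst post-baseline value, stating for each parameter which direction is worst.
- Add the laboratory shift tables of Protocol 14.4.1, using all post-baseline records. Screening is the only planned pre-dose laboratory draw in either part, so it supplies the starting category.
- State that, with these rows, laboratory tests and vital signs are summarised on the scope given in Protocol 14.3.

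The cost is SAP wording, some programming and a few extra table rows, with no new assessments. The drawback is that the last-value row mixes different treatment durations, and in Part 1 a completer's last value comes at Day 42, four weeks after treatment. The row should be labelled accordingly and read beside the by-visit rows. Protocol 10.6.5 does not list the lipid panel for the Unanticipated Visit, so lipid rows may gain less.

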### **2.3.3. Prior and Concomitant Medications**

Prior and concomitant medications will be summarized by frequencies and percentages. All medications will be coded using the World Health Organization (WHO) Drug dictionary September 2017 version.

Prior medications will be defined as any medication that started prior to the first day of administration. Concomitant medications will be defined as any medication that starts or is ongoing on or after the first day of administration. A medication may qualify as both a prior and concomitant medication if it started prior to first day of administration and is ongoing or stopped after the first day of administration.

Section 2.8 describes the imputation rules for partial dates. All medications will be presented in a data listing.

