### **2.4.1. Adverse Events / Serious Adverse Events**

Adverse events will be coded using the medical dictionary of regulatory activities (MedDRA Version 20.1) dictionary.

Treatment-emergent adverse events (TEAEs) will be defined as any AE that starts on or after the first administration of study medication. Any event that started prior to the first administration of study medication but worsened in severity after the first administration will be recorded as a new event so that it may be captured as a TEAE. AEs with an unknown onset date will be counted as treatment-emergent unless the event resolved prior to the first administration. Section 2.8 describes the imputation rules for partial dates.

Treatment-emergent adverse events that are documented as occurring within 30 minutes after any of the doses will be summarized with the other TEAEs and separately from the other TEAEs.

The incidence of TEAEs will be presented by system organ class (SOC) and preferred term (PT). Events will also be summarized by severity and relationship. The incidence of TEAEs leading to withdrawal from the study and SAEs, including deaths, will be presented in both summary tables and data listings.

All AEs will be presented in data listings.

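### SAP 2.8 moves some partial start dates to the first-dose date without checking a known stop date, so a medicine stopped before dosing is tabulated as concomitant and, on one reading, a resolved adverse event becomes treatment-emergent

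*SAP*

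**What the plan says.** SAP 2.8 (Safety and Other Rules) gives three rules for incomplete start dates of adverse events and medications.

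- Day missing, with the known month and year matching the first dose: "impute the day to be equal to the day of the first injection"; in all other cases the first of the month is used.
- Month missing, year equal to the first-dose year: "impute the month and day of the date to be equal to the first injection month and day"; otherwise January is used.
- Year missing: "If the year is unknown, then the start date will not be imputed".

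The section contains one plausibility limit, and it concerns stop dates: "If an imputed stop date is greater than the date of study completion/discontinuation date of the study", the stop is pulled back to that date. No limit ties an imputed start to the record's own stop.

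The imputed dates feed two classifications. SAP 2.3.3 states: "Concomitant medications will be defined as any medication that starts or is ongoing on or after the first day of administration". A prior medication is one that began before that day. SAP 2.4.1 makes an adverse event treatment-emergent (a TEAE) if it starts at or after first administration, and adds: "AEs with an unknown onset date will be counted as treatment-emergent unless the event resolved prior to the first administration". Its next sentence refers partial dates to SAP 2.8.

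**The concern.** Moving an ambiguous start to the first-dose date is a common and deliberately cautious convention when it is unclear whether a record belongs before or after dosing. It stops being cautious when the stop date already settles the matter. A record that ended before dosing cannot have begun on the dosing day, yet the rule assigns it that start.

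For medications nothing later in the SAP corrects this: 2.3.3 classifies on the start or on ongoing status and has no exception for a known earlier stop. The record appears in the concomitant table (14.1.4.2) and is lost from the prior table (14.1.4.1).

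For adverse events, safety is the primary endpoint in Part 1 and a secondary endpoint in Part 2, and the arms are small, so one wrongly classed event is visible in the incidence tables. Pre-dose events are plausible. Safety events are collected at screening in both parts and at the Part 2 titration visit (Protocol 10.5.1, 10.6.1, 10.6.2), and in Part 2 two allergen challenges precede the first dose.

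**Working it through.** The plan states no figure to reproduce here. The check applies the SAP 2.8 start-date rules literally and then the definitions in SAP 2.3.3 and 2.4.1.

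**Worked cases.** Assumed first dose: 20 February 2018.

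| Recorded start | Known stop | Imputed start | Stop minus imputed start | Medication class | AE, by the start rule alone |
|---|---|---|---|---|---|
| Feb 2018, day missing | 5 Feb 2018 | 20 Feb 2018 | −15 days | concomitant, not prior | TEAE |
| 2018, month missing | 15 Jan 2018 | 20 Feb 2018 | −36 days | concomitant, not prior | TEAE |
| Jan 2018, day missing | 5 Feb 2018 | 1 Jan 2018 | +35 days | prior only | not TEAE |
| 2017, month missing | 5 Feb 2018 | 1 Jan 2017 | +400 days | prior only | not TEAE |
| year missing | 5 Feb 2018 | none | – | no rule in 2.3.3 | not TEAE (2.4.1 exception) |

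The error arises only in the first two rows, the branches that impute to the first-dose date. The other branches give the right class.

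**Enumeration of the same-month branch.** Take every first-dose date from September 2017 to March 2018 (the study period in the protocol synopsis) and every pair with true start ≤ known stop < first dose in the same month. A first dose on day d gives d(d−1)/2 pairs. The monthly totals are 4,495 (30 days), 4,960 (31 days) and 3,654 (28 days). Sum: 2 × 4,495 + 4 × 4,960 + 3,654 = 32,484.

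- Rule as written: 32,484 of 32,484 pairs get a start on the first-dose date.
- Start taken as the earlier of first-dose date and known stop: 0 of 32,484.

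This follows from the logic of the rule. It shows that the error is certain within the branch, not how often the branch is used.

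**The adverse-event rule.** The 2.4.1 exception speaks of an unknown onset date, and partial dates are then sent separately to 2.8.

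- Narrow reading: the exception covers only dates left missing (year unknown). A partial onset has already been filled, so the first two rows become TEAEs.
- Broad reading: an onset with a missing day is also unknown, so the exception applies and both events stay out.

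The SAP supports either reading. Two programmers could produce different TEAE tables from the same data.

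**Size if one subject is affected on the narrow reading.** Planned group sizes are from SAP 2.7.

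- Active Part 1 cohort: 1/8 = 12.5 percentage points.
- Part 2 arm: 1/14 = 7.1 percentage points.

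**The case against.** The strongest defence is that the practical reach is small, and much of it stands.

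- **Adverse events.** SAP 2.4.1 does contain a stop-date check, and 2.8 says that dates are imputed in order to classify records properly. A sensible programmer could apply the check to partial onsets. A reader might infer that false TEAEs will certainly enter the safety tables; the text supports only that they may.
- **Few partial dates.** Start and stop dates must be recorded for every event (Protocol 15.4), events go into a daily diary (11.17), and missing data are queried (18.4). Reporting is defined from the first dose onward (15.3), although events are also collected at earlier visits. This makes affected adverse-event records uncommon but does not exclude them.
- **Per-protocol set.** A reader might infer that a washed-out drug flagged as concomitant would count as prohibited use and remove the subject from the per-protocol set. The documents do not support this. Deviations are supplied by the clinical team (SAP 2.10), listings show observed dates only, and original dates are stored beside imputed ones (2.8). Anyone judging prohibited use would see the recorded stop.
- **Antihistamines in Part 2.** These look like the natural example, given the one-week restriction in Protocol 6.4. But the Part 2 first dose falls at Visit 3, nominally 14 days after titration. With a first dose on 20 January, titration is on 6 January, so use until 8 January is on-protocol use and not a completed washout. For drugs restricted for a month or longer, essentially only the year-only branch could apply.
- **An error rate near one half.** With first-dose days spread evenly over a 30-day month, the mean of (d−1)/30 is 0.483. A reader might take 48% as the share of records misclassified. It is only the share of calendar days before dosing.

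None of this answers the medication rule. It applies to any recorded medicine, and no other section of the SAP corrects the class.

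**Conclusion.** The point holds in a limited form. For medications it is a definite error of derivation: with a start that matches the first-dose month and year (or the year alone, if the month is missing) and a known stop before first dose, the record always gets a start after its stop and is classed as concomitant and not prior. The direct harm is a wrong row in descriptive tables.

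For adverse events it is an unresolved ambiguity. Only if the 2.4.1 exception is confined to wholly missing dates does a resolved pre-dose event become a TEAE. One such subject would then add 12.5 points in an active Part 1 cohort of 8 or 7.1 points in a Part 2 arm of 14. Those figures assume full planned enrolment and that such an event occurs in a subject who would not otherwise count for that incidence.

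The number of affected records cannot be derived from the documents. This is a minor clarification, worth making before the tables are programmed.

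**What to change.** 1. In SAP 2.8, in the two branches that impute to the first-dose date and only there, set the start to the earlier of the first-dose date and the known stop date. Leave the January and day-01 branches unchanged. The restriction matters. Take a start in December with the day missing, a first dose on 20 January and a stop on 25 January. The present rule correctly gives 1 December. Applied to every partial start, the earlier-of rule would give 20 January and create a false TEAE.
2. In SAP 2.3.3 and 2.4.1, state that a medication or adverse event with a known stop before first administration is prior, or not treatment-emergent, including when its start date is partial. This also gives 2.3.3 a rule for medicines whose start year is missing.
3. In SAP 2.8, replace the references to a first injection with first administration of study medication, since the product is a nasal spray. This is a wording correction only.

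The cost is a few SAP sentences and about one line of derivation code. No data collection or study procedure changes.
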